## **5.2.6 Follow-up Period (All Subjects)**

### **5.2.6.1 30-Days (Plus 3 days) After Last Treatment**

The following evaluations will be performed 30 days (+ 3 days) after the last treatment as specified:

- 1) Perform complete physical examination (if applicable, record new findings as AEs or SAEs)
- 2) Assess survival status and AEs and SAEs since the time of discontinuation until the subject begins another anticancer therapy
- 3) Obtain vital signs (temperature, blood pressure, pulse, respiratory rate) including weight
- 4) Assess ECOG performance status
- 5) Obtain 12-lead ECG
- 6) Collect blood samples for:
  - Serum chemistry
  - Hematology
  - Anti-MEDI-575 antibodies
  - MEDI-575 serum concentration
  - Circulating soluble proteins
  - Circulating apoptotic markers
- 7) Collect urine for routine urinalysis
- 8) Update concomitant medications; ascertain whether subsequent anticancer therapy has been initiated

### **5.2.6.2 60 and 90 Days (Plus or Minus 5 Days) After Last Treatment**

The following evaluations will be performed 60 and 90 days ( $\pm$  5 days) after the last treatment as specified:

- 1) Perform complete physical examination (if applicable, record new findings as AEs or SAEs)
- 2) Assess survival status, AEs, and SAEs since the time of discontinuation until the subject begins another anticancer therapy
- 3) Obtain vital signs (temperature, blood pressure, pulse, respiratory rate) including weight
- 4) Assess ECOG performance status
- 5) Collect blood samples for:
  - Serum chemistry
  - Hematology
  - Anti-MEDI-575 antibodies
  - MEDI-575 serum concentration
  - Circulating soluble proteins
  - Circulating apoptotic markers
- 6) Collect urine for routine urinalysis and urine pregnancy test (women of childbearing potential only (90-day post visit only)).
- 7) Record subsequent anticancer therapy

### **5.2.6.3 Every 3 Months (Plus or Minus 14 Days) After Last Treatment**

The following evaluations will be performed every 3 months ( $\pm$  14 days) after the last treatment as specified (for subjects who discontinue treatment due to reasons other than disease progression or initiation of alternative anticancer therapy, these evaluations will be performed until documentation of disease progression, initiation of alternative anticancer therapy, or the end of study [defined as 9 months post the date the last subject is entered on the trial or when sponsor stops the study]):

- 1) Evaluation of disease
  - MRI scan
  - Focused physical examination
  - ECOG performance status

- 2) Blood collection for anti-MEDI-575 antibodies (3-month post visit only)
- 3) Survival status and subsequent anticancer therapy must be collected in every subject regardless of the reason for treatment discontinuation. Assessment can be either performed on a clinic visit or telephone contact until death or the end of the study

### **5.3 Description of Study Procedures**

A laboratory manual will be provided to the sites that specifies the procedures for collection, processing, storage, and shipment of samples, as well as laboratory contact information.

#### **5.3.1 Medical History, Physical Examination, ECG, Weight, and Vital Signs**

Complete physical examinations will be performed as described in [Table 5.2-1](#) and [Table 5.2-2](#) by a licensed independent healthcare provider (ie, physician, physician's assistant, or licensed nurse practitioner). It will include an assessment of head, eyes, ears, nose and throat, respiratory, cardiovascular, gastrointestinal (GI), urogenital, musculoskeletal, neurological, psychiatric, dermatological, hematologic/lymphatic, and endocrine systems; and height (at screening only).

Vital signs will be collected as described in [Table 5.2-1](#) and [Table 5.2-2](#). Vital signs include temperature, blood pressure (seated), pulse rate, and respiratory rate and weight (when indicated).

Twelve-lead ECGs will be performed as described in [Table 5.2-1](#) and [Table 5.2-2](#). Electrocardiograph equipment, with instant print-out and electronic transmission capabilities, and training will be provided to all study sites. All ECGs performed during the study will be obtained in triplicate (ie, 3 ECGs should be obtained within a 5-minute time period). The electrocardiograms will be transmitted and interpreted by a central vendor selected by the sponsor.

#### **5.3.2 Clinical Laboratory Tests**

Clinical laboratory safety tests including serum pregnancy tests will be performed in a licensed clinical laboratory. Clinically significant abnormal laboratory tests should be repeated as soon as possible (preferably within 24 to 48 hours). Clinically significant abnormal labs should be repeated subsequently at the investigator's discretion. These tests can be collected up to 1 day in advance of treatment Day 1 in each cycle.

The following clinical laboratory tests will be performed (see [Table 5.2-1](#) and [Table 5.2-2](#) for the schedule of tests):

### Serum Chemistry

- Calcium
- Chloride
- Magnesium
- Potassium
- Sodium
- Aspartate transaminase (AST)
- Alanine transaminase (ALT)
- Alkaline phosphatase (ALP)
- Gamma glutamyl transferase (GGT)
- Lactic dehydrogenase (LDH)
- Carbon dioxide/bicarbonate
- Blood urea nitrogen (BUN)
- Uric acid
- Creatinine
- Total bilirubin
- Glucose
- Albumin
- Total protein
- Triglycerides
- Cholesterol
- Phosphorous

Note for serum chemistries: Tests for AST, ALT, ALP, and total bilirubin must be conducted concurrently and assessed concurrently.

### Hematology

- White blood cell (WBC) count with differential
- Red blood cell (RBC) count
- Hematocrit
- Platelet count
- Hemoglobin

### Urinalysis

- pH
- Protein
- Blood
- Glucose
- Ketones
- Bilirubin

### Pregnancy Test (women of childbearing potential only)

- Urine human chorionic gonadotropin (hCG)
- Serum  $\beta$ HCG (at screening only)

### Other Safety Tests

- Coagulation parameters: prothrombin time (PT), partial thromboplastin time (PTT), and fibrinogen, international normalized ratio (INR)

### **5.3.3 Pharmacokinetic Evaluation and Methods**

The timepoints for PK sampling are described in [Table 5.2-1](#) and [Table 5.2-2](#). A competitive electrochemiluminescence assay using a Meso Scale Discovery® (MSD) platform will be used for the quantitative determination of MEDI-575 in human serum.

Details of PK sample collection are provided in the laboratory manual.

### **5.3.4 Immunogenicity Evaluation and Methods**

Presence of anti-MEDI-575 antibodies will be assessed prior to infusion of MEDI-575 on Day 1 of each cycle as well as at the end of treatment and during follow up. Details for sample collection will be provided in the laboratory manual.

### **5.3.5 Biomarker Evaluation and Methods**

Blood samples will be analyzed to evaluate protein, deoxyribonucleic acid (DNA), and mRNA/miRNA biomarkers that relate to MEDI-575 treatment. For the assessment of MEDI-575 pharmacodynamic activity, plasma levels of PDGF-AA ligand will be measured at baseline and in response to MEDI-575 treatment. In addition to evaluating circulating levels of PDGF-AA, multiplex protein analysis may be utilized to evaluate circulating levels of soluble proteins related to tumor-associated factors, angiogenesis, and growth factors that may include, but are not limited to, PDGF, fibroblast growth factor (FGF), VEGF, fibronectin, osteopontin, transforming growth factor (TGF), and hepatocyte growth factor (HGF), and to explore their association with MEDI-575 treatment and clinical outcome. Circulating apoptotic markers will be evaluated by determining nucleosomal DNA levels at baseline and in response to treatment using either an enzyme linked immunosorbent assay (ELISA) or reverse transcription polymerase chain reaction (RT-PCR) as a biomarker for tumor apoptosis. Messenger RNA profiling from whole blood samples may be performed and gene expression analysis will examine the potential relationship between inhibition of PDGF-related genes, clinical activity, and other circulating factors. Additionally, the miRNA expression pattern in the periphery of subjects enrolled may be examined.

In tissue samples which have been collected prior to study entry (mandatory archival samples), expression of PDGF signaling protein by immunohistochemistry (IHC) analysis may include, but is not limited to, PDGFR $\alpha$ , PDGF ligands, and EGFR. Additionally, for tumor cells that stain intensely for PDGFR $\alpha$ , an analysis of genomic amplification may be

performed. The expression level of PDGFR $\alpha$  in tumor cells and tumor stroma including intensity of staining and distribution of staining will be evaluated for any relationship to treatment with MEDI-575.

If fresh tumor biopsy samples obtained following discontinuation of treatment with MEDI-575 are available (optional), the presence of MEDI-575 in the tumor tissue will be evaluated using IHC, ELISA, or mass spectrometry. If sufficient tissue is collected then the relationship of growth factor receptor pathways and related components at the protein mRNA and miRNA levels may be evaluated from tumor biopsies obtained post-treatment using IHC, proteomic analysis, TaqMan QRT-PCR assays, and/or microarray studies. These factors may include but are not limited to, PDGFR, EGFR, insulin-like growth factor-1 receptor (IGF1R), VEGFR2, and associated growth factors (PDGF, HGF, VEGF, FGF, insulin-like growth factor [IGF], and interleukins). These studies serve the purpose of evaluating MEDI-575 drug levels in the tumor and, if possible, molecular characteristics of the tumor and relationship with MEDI-575 treatment. If enough tumor tissue and blood samples are available, a competitive allele-specific TaqMan-based-PCR assay will be used to evaluate potential point mutations in the key genes such as PDGFR $\alpha$ , EGFR, phosphoinositide 3-kinase (PI3k), phosphatase and tensin homolog and their correlations with clinical activity of MEDI-575. Additionally, the TaqMan low density array based assays may be used to evaluate miRNA profile in the tissue, plasma and/or whole blood of patients pre- and post-MEDI-575 dosing.

Other biomarkers may be evaluated as determined by additional data. Details for collection will be provided in the laboratory manual.

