## 3 Study Design

### 3.1 Overview of Study Design

This is a Phase 2, multicenter, open-label, single-arm study to evaluate the antitumor activity, safety, and pharmacology of MEDI-575 in adult subjects with first recurrence of GBM.

Approximately 55 subjects will be enrolled to determine the preliminary efficacy profile of MEDI-575 in the treatment of subjects with first recurrence of GBM. Subjects will receive MEDI-575 as a 60-minute IV infusion on Day 1 every 21 days until disease progression, initiation of alternative anticancer therapy, unacceptable toxicity, or other reasons for subject withdrawal (see Section 4.2.3) (Figure 3.1-1). In Cycle 2 and beyond, a dose can be delayed up to 7 days for unavoidable scheduling issues. MEDI-575 may be withheld for up to 21 days until resolution to  $\leq$  Grade 1 toxicity after agreement with the sponsor. The primary assessment of antitumor activity is PFS-6; progression will be determined using *Updated Response Assessment Criteria of High Grade Gliomas- Neuro-Oncology Working Group v.1* (see Appendix 5) (Wen et al, 2010). Approximately 15 investigational sites in the United States (USA) will participate in this study. Subjects who receive any amount of MEDI-575 and proceed to subsequent surgery as therapy for GBM (at second recurrence/disease progression) will be requested to allow use of surgically resected tissue for analysis of intratumoral levels of MEDI-575.

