#### **4.5.2 Treatment Regimens**

Subjects will be treated with MEDI-575 at 25 mg/kg on Day 1 every 21 days until documentation of disease progression, initiation of alternative anticancer therapy, unacceptable toxicity, or another reason for treatment discontinuation (see Section 4.2.3) is observed. In Cycle 2 and beyond, a dose can be delayed up to 7 days for unavoidable scheduling issues. MEDI-575 may be withheld for up to 21 days until resolution to  $\leq$  Grade 1 toxicity after agreement with the sponsor. Subjects who demonstrate stable disease or better may continue to receive MEDI-575 under the criteria above. Each new cycle will begin no fewer than 21 days after the last dose of the previous cycle.

Subjects who receive any number of doses of MEDI-575 and proceed to surgical resection as subsequent therapy for GBM may be asked to allow procurement of resected tissue to determine intratumoral levels of MEDI-575.

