**Table 5.2-1 Schedule of Study Procedures: Screening and Treatment Period**

Procedure	Screening	Treatment Period Cycle 1			Cycles $\geq$ 2	Every 2 Cycles, Beginning With Cycle 3	Treatment Discontinuation
	Day -28 to Day -1	Day 1	Day 8	Day 15	Day 1 (+7 days)	Day 1 (-7 days)	
MEDI-575 administration		X			X		
Optional tumor tissue sample							X

AE = adverse event; DNA = deoxyribonucleic acid, ECG = electrocardiogram, ECOG = Eastern Cooperative Oncology Group, EORTC = European Organization of Research and Treatment of Cancer, HIPAA = Health Insurance Portability and Accountability Act, mRNA = messenger ribonucleic acid; miRNA = micro ribonucleic acid; MRI = magnetic resonance imaging, PRO = patient reported outcomes, QLQ = quality of life questionnaire; RNA = ribonucleic acid; SAE = serious adverse event ; SID = subject identification

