### **5.2.5 Treatment Discontinuation Visit**

The following evaluations will be performed at the time (or up to 5 days after) the subject completes therapy or is withdrawn/discontinued from the study therapy, or at the time of first objective disease progression, whichever comes first. Any procedures conducted within 14 days before treatment discontinuation (eg, procedures conducted on Day 1 of a cycle) do not need to be repeated at the treatment discontinuation visit.

- 1) Perform complete physical examination (if applicable, record new findings as AEs or SAEs)
- 2) Assess for AEs and SAEs
- 3) Update concomitant medications
- 4) Obtain vital signs (temperature, blood pressure, pulse, respiratory rate) including weight (-1 day allowed for weight)
- 5) Assess ECOG performance status
- 6) Collect blood samples for:
  - Serum chemistry (-1 day allowed)
  - Hematology (-1 day allowed)
  - Coagulation parameters (-1 day allowed)
  - Anti-MEDI-575 antibodies
  - MEDI-575 serum concentration
  - Circulating soluble proteins
  - Circulating apoptotic markers
  - Circulating mRNA/miRNA
- 7) Collect urine for routine urinalysis (-1 day allowed)
- 8) Perform 12-lead ECG

- 9) Obtain consent and collect fresh tissue tumor biopsy (optional)
- 10) Administer PRO questionnaires (-3 days allowed)
  - EORTC QLQ-C30
  - EORTC QLQ-BN20
- 11) Disease evaluations:
  - MRI scan

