#### Section 4.2.3 (Withdrawal Criteria)

#### Section 5.2.6.2 (60 and 90 Days (Plus or Minus 5 Days) After Last Treatment):

#### Section 6.4.1 (Study Reporting Period and Follow-up for Adverse Events)

#### Section 6.4.2.1 (Study Reporting Period and Follow-up for Serious Adverse Events)

#### Section 7.3.2.2 (Secondary Endpoints of Safety and Tolerability of MEDI-575)

The safety follow up period is being extended to 90 days to ensure that the MEDI-575 level is lower than the lower limit of quantification

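### Resected tumor tissue can be taken at any time after the last dose with no serum sample at surgery, so a negative MEDI-575 result from that route cannot separate non-penetration from washout

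*Protocol*

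**What the plan says.** The protocol has two routes to tumor tissue after treatment.

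- **Resection.** Section 3.1 covers "Subjects who receive any amount of MEDI-575 and proceed to subsequent surgery as therapy for GBM", placing surgery at second recurrence or progression. Section 4.5.2 repeats the rule for "Subjects who receive any number of doses of MEDI-575 and proceed to surgical resection as subsequent therapy for GBM". Neither sets a maximum interval from the last dose or names a blood sample at surgery.
- **Discontinuation biopsy.** Table 5.2-1 lists "Optional tumor tissue sample" at the Treatment Discontinuation visit only. Section 5.2.5 lists the optional fresh biopsy and a MEDI-575 serum concentration at that same visit.

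Section 5.3.5 is where the assay is named: "the presence of MEDI-575 in the tumor tissue will be evaluated using IHC, ELISA, or mass spectrometry". That sentence is worded for fresh biopsies after discontinuation. The stated aim is broader: "These studies serve the purpose of evaluating MEDI-575 drug levels in the tumor".

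In follow-up, Table 5.2-2 schedules serum MEDI-575 at 30, 60 and 90 days after the last dose, none at the 3-monthly visits, and no tissue at any visit. Section 15 explains that the safety follow-up was extended to 90 days to "ensure that the MEDI-575 level is lower than the lower limit of quantification".

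**The concern.** Section 3.4 acknowledges that antibodies of this size generally do not cross the blood-brain barrier and that adequate levels in GBM may be hard to reach. It concedes that its supporting antibody data are not specific to GBM. Exploratory objective 4 is the trial's direct measurement on that question.

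A tissue result can be read only against the drug circulating when the tissue was removed. If serum was high and tissue is negative, the result bears on penetration. If serum had already gone, the same result says nothing. For a resection outside the discontinuation visit, the plan does not secure the information that tells these cases apart, and a level that was never drawn cannot be recovered at analysis. Few subjects are likely to have surgery, so each uninterpretable sample is a real loss to this objective.

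**Working it through.** **Which samples are paired**

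| Tissue source | Tissue in schedule | Serum at the same time |
|---|---|---|
| Biopsy at Treatment Discontinuation | Yes, Table 5.2-1 | Yes, Section 5.2.5, though a sample from the 14 days before discontinuation may stand in |
| Resection, up to 90 days after last dose | None | None tied to surgery; days 30, 60 and 90 only |
| Resection, after 90 days | None | None |

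**How fast serum falls**

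The protocol gives no washout curve to reproduce, so this is an illustration.

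Inputs from the protocol (Section 1.2.3 unless stated):
- Michaelis constant KM = 7.88 µg/mL; maximum nonlinear intrinsic clearance CLint = 2.22 L/day.
- The receptor sink carries more than 90% of clearance when unsaturated. So 2.22/(2.22 + CL) > 0.9, which gives linear clearance CL < 2.22/9 = 0.247 L/day.
- 25 mg/kg every 21 days (Section 4.5.2), with a steady-state trough expected above 150 µg/mL.

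Assumptions, because the document gives no values: CL 0.15-0.247 L/day, volume V 4-6.5 L, weight 75 kg (dose 25 × 75 = 1,875 mg), one compartment, infusion treated as instantaneous.

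Model: dC/dt = −(CL/V)·C − (CLint·KM/V)·C/(KM + C).

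Hand check with V = 4 and CL = 0.20. The maximum saturable rate is 2.22 × 7.88/4 = 4.37 µg/mL per day. At C = 100 the total loss is 0.05 × 100 + 4.37 × 100/107.88 = 9.05 µg/mL per day, an instantaneous half-life of 0.693/0.0905 = 7.7 days. Well below KM the rate is (0.20 + 2.22)/4 = 0.605 per day, a half-life of 1.1 days. Elimination therefore speeds up as the level drops.

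Serum in µg/mL after the sixth dose:

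| V (L) | CL (L/day) | Day 21 | Day 30 | Day 40 | Day 60 | Day 30 ÷ day 60 |
|---|---|---|---|---|---|---|
| 4 | 0.15 | 274 | 164 | 78 | 0.7 | 230 |
| 4 | 0.20 | 167 | 77 | 18 | <0.1 | >1,000 |
| 4 | 0.247 | 108 | 35 | 2 | <0.1 | >1,000 |
| 5.25 | 0.15 | 311 | 215 | 134 | 31 | 7.0 |
| 5.25 | 0.20 | 204 | 121 | 57 | 1.0 | 127 |
| 5.25 | 0.247 | 143 | 71 | 22 | <0.1 | >1,000 |
| 6.5 | 0.15 | 329 | 246 | 172 | 69 | 3.6 |
| 6.5 | 0.20 | 228 | 152 | 90 | 16 | 9.7 |
| 6.5 | 0.247 | 166 | 99 | 48 | 1.4 | 69 |

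Two rows give a day-21 level below the protocol's 150 µg/mL (108 and 143). Dropping them leaves day 30 at 77-246, day 40 at 18-172 and day 60 at <0.1-69, and the smallest fall is still 3.6-fold.

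**Second start point.** Starting instead from exactly 150 µg/mL at day 21, with V 3-6 L and CL 0.10-0.247 L/day, serum is about 38-106 at day 30 and 0-9 at day 60. It crosses KM at about day 35-61. A trough above 150 would lengthen this.

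**Single exposure.** Sections 3.1 and 4.5.2 also accept one dose. In the nine settings above, day 40 after a single dose is about 0.3-49 µg/mL.

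So surgery between days 30 and 60 can fall anywhere from substantial circulating drug to almost none, and neither neighboring scheduled sample stands in for it. The document gives no interval from progression to surgery, so the share of resections in that range is unknown.

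**The case against.** The strongest reply is that much of this is already covered. The one scheduled tissue time point has a serum level beside it. Serum is drawn before and after infusion in every cycle, at discontinuation, and at days 30, 60 and 90. Section 7.3.3.1.2 plans a population PK model with linear and target-mediated clearance, which can estimate the level on a given day of surgery. Collection details are left to a laboratory manual that is not shown. The tissue is optional and the objective exploratory.

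Most of that stands, and it sets the limits of the point. What it does not answer is this. The model can approximate serum only within the sampled 90 days, the protocol does not link it to reading tissue, and prediction is least certain near KM, where elimination accelerates. After day 90 no serum is scheduled at all. A blood draw at surgery is a study procedure and belongs in the protocol schedule, whatever the laboratory manual says about handling.

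Two stronger readings are tempting. A reader might infer that no tissue result can be interpreted; the serum level listed at the discontinuation visit rules that out, and a positive result from any route remains informative. A reader might also infer that a negative PFS-6 result would stay unexplained because of this gap. That does not follow: a few optional exploratory samples would not explain the primary result even with perfect pairing.

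**Conclusion.** The point holds for resections outside the Treatment Discontinuation visit. For those the protocol sets no time limit, ties no serum sample to surgery and has no schedule entry, so a negative tissue result cannot separate non-penetration from washout.

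Between days 30 and 60 the modeled serum level falls at least 3.6-fold, and more than 100-fold in five of the nine settings. The exact figures rest on assumed linear clearance, volume and weight and on a one-compartment model. The direction rests on the protocol's own saturable clearance and on its expectation that drug is unquantifiable by day 90.

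This is a low-cost improvement to exploratory objective 4. The primary analysis is not touched.

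**What to change.** Add an at-resection entry to Table 5.2-2 with the tissue sample, the dates of last dose and of surgery, and one MEDI-575 serum sample taken from the pre-operative blood draw. Cross-refer to it from Sections 3.1, 4.5.2 and 5.3.5.

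In the analysis:
- Report each tissue level with its paired serum level.
- Use the population PK prediction only where no serum was drawn and surgery fell within the sampled period, and label it as predicted.
- Read a negative tissue result as evidence on penetration only when paired serum is well above the quantification limit. Set the margin in advance from the serum and tissue assay limits, which the protocol does not give. Serum that is merely quantifiable is too weak a condition, because a level just above the limit would still leave washout and tissue-assay insensitivity open.

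The cost is one extra tube in the few subjects who have surgery, and some tissue results will be classed as uninformative.
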